14.2 Primary Efficacy Endpoint

The primary efficacy endpoint is change from baseline in standing height/body length Z-Score at Week 52.

Each measurement of derived standing height/body length will be converted to an age-and sex-appropriate standard deviation score (SDS), also referred to as a Z-Score, by comparison with reference data available for average stature children from the CDC. Note no data conversions are applied between body length and standing height as recommended for average stature.

Standing height/body length Z-Scores will be derived using CDC references and macro ([CDC, 2019](#)).

14.2.1 Primary Analyses

The standing height/body length Z-Score at 6 Months Prior to baseline, 3 Months Prior to baseline for Cohort 3, baseline, Week 26 and Week 52, and its change from baseline at Week 26 and Week 52 will be summarized and presented separately by cohort by treatment group using format as specified in [Table 5.1](#), [Table 5.2](#), and [Table 5.3](#) for Cohorts 1, 2, and 3, respectively.

Height Z-Scores derived for all visits from 111-901 and 111-206 will be included in data listings.

A line plot of individual standing height/body length Z-Score will be presented at baseline and Week 52 for each subject by cohort by stratified age stratum. A line plot of the mean (+/- SD) standing height/body length Z-Score will be presented by cohort at 6 Months Prior (3-month prior for Subjects in Cohort 3), Baseline, Week 26 and Week 52.

For the model-based ANCOVA analyses, estimand formulation is as follows:

- Population: All randomized subjects in FAS overall and/or by cohort as appropriate
- Variable: Change from baseline in standing height/body length Z-Score at Week 52
- Intercurrent event: Regardless of whether or not switching to rescue medication had occurred or subjects had discontinued from the treatment. See Section 14.1 for handling of missing data
- Population-level summary: Lsmean difference and 95%CI between the treatment groups based on ANCOVA models defined in Section [14.1](#)

ANCOVA model will include the fixed-effects of treatment (active arm vs. placebo arm) and baseline covariates, where baseline covariates include randomization age stratum, age at baseline, sex, baseline AGV, and baseline height Z-Score. The following SAS Proc Mixed with option OBSMARGINS for lsmeans will be used to perform the analysis on all randomized subjects in FAS overall and/or by cohort by each imputed dataset:

```
PROC MIXED;  
  
CLASS Treatment Sex Age_stratum;  
  
MODEL Change from baseline in height Z-Score at Week 52 = Treatment  
Age_baseline Sex Age_stratum AGV_baseline Height Z-Score_baseline;  
  
LSMEANS Treatment / DIFF CL OM;  
  
ESTIMATE 'Active - Placebo' Treatment 1 -1/CL;  
  
RUN;
```

For the models that will include the data from the multiple imputation a “by imputation statement will be included” and then PROC MIANALYZE will be used to combine the estimates from each of the mixed models.

These analyses will be repeated by also including sentinel subjects from the corresponding cohort.

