4.2 Study Design

Study 111-206 is a phase 2 stratified randomized, double-blind, placebo-controlled clinical trial of vosoritide in infants and younger children with a diagnosis of ACH.

Subjects aged ≥ 6 months to < 60 months old who have documented ACH confirmed by genetic testing; at least a 6-month period of pretreatment growth assessment in Study 111-901 immediately before study entry; and who meet the study eligibility criteria, will participate. Eligible subjects ranging from 0 months to < 3 months old may enroll directly into 111-206 and have a minimum of 3 months of pre-treatment observation prior to commencing treatment with investigational product or may enroll in 111-901 for a minimum of 3 months of pretreatment growth assessment immediately before roll-over to 111-206.

Approximately 70 subjects will be enrolled at approximately 10-15 clinical centers worldwide.

Subjects will be enrolled into 3 age cohorts based on age at study screening starting with the eldest population. Within Cohorts 1 and 2, subjects will be stratified by age:

- Cohort 1 – children aged ≥ 24 to < 60 months ($n \geq 30$ total: 3 sentinel subjects who receive vosoritide, and at least 27 additional subjects randomized 1:1 to treatment or placebo control), stratified by age (≥ 24 months to < 36 months and ≥ 36 months to < 60 months)
- Cohort 2 – children aged ≥ 6 to < 24 months ($n \geq 20$ total: 3 sentinel subjects who receive vosoritide, and at least 17 additional subjects randomized 1:1 to treatment or placebo control), stratified by age (≥ 6 months to < 15 months and ≥ 15 months to < 24 months)

- Cohort 3 – children aged 0 to < 6 months (n ≥ 20 total: 3 sentinel subjects who receive vosoritide, and at least 17 additional subjects randomized 1:1 to treatment or placebo control). Treatment begins at ≥ 3 months to < 6 months after 3 months of observation.

[figure not shown]
Sentinel subjects from each cohort will be enrolled, treated with vosoritide, and studied for short-term safety and PK data. After the sentinel data are evaluated within a cohort additional recruited subjects will be randomized to receive vosoritide or placebo subcutaneous daily (1:1 ratio) for 52 weeks.

As subjects age on study, they will be administered the dose determined to be appropriate for their current age as follows:

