Results of the statistical analyses will be provided in separate tables, including the least-squares (LS) mean change from baseline at Week 52 for each treatment group, the treatment difference in LS means (calculated as vosoritide - Placebo), the 95% confidence interval (CI) for the treatment difference, and corresponding 2-sided p-value.

Listings for standing height/body length and standing height/body length z-score will include all assessments (i.e., all measures and means of the measures) and spaghetti plots for height and height Z-Score will include assessments every 6 months and will be ordered by cohort,

sentinel/randomized subject, treatment, subject ID and visit date including 111-901 and 111-206.

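### Section 14.2.1 pools the imputed ANCOVAs without setting complete-data degrees of freedom, so by-cohort results with about 10 to 20 residual df are read against a near-normal reference

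*SAP*

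**What the plan says.** In SAP Version 2, Section 14.1, a missing Week 52 value is interpolated if a later assessment exists. Otherwise it is multiply imputed from placebo children in the same cohort. Section 14.2.1 fits PROC MIXED to each imputed dataset and then states that "PROC MIANALYZE will be used to combine the estimates from each of the mixed models". The population is "All randomized subjects in FAS overall and/or by cohort as appropriate", and the "baseline covariates include randomization age stratum, age at baseline, sex, baseline AGV, and baseline height Z-Score".

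Section 14.1 reports "the 95% confidence interval (CI) for the treatment difference, and corresponding 2-sided p-value". Sections 14.3.1 to 14.3.3 apply the same methods to standing height/body length, cumulative AGV and the upper-to-lower segment ratio.

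Section 4.2 sets the randomized numbers. Cohort 1 has "at least 27 additional subjects randomized 1:1 to treatment or placebo control), stratified by age" and Cohort 2 has "at least 17 additional subjects randomized 1:1 to treatment or placebo control), stratified by age". Cohort 3 has the same minimum of 17, and Section 4.6.2 names only Cohorts 1 and 2 as stratified.

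Neither Section 14.1, Section 14.2.1 nor the change table in Section 24 gives a degrees-of-freedom rule for the pooled estimate, an EDF= value or the number of imputations.

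**The concern.** When no complete-data df is supplied, the standard combining rule treats it as infinite. The pooled df then depends only on the number of imputations and on how much variance the imputation adds, and not on the number of children. With one or two imputed heights the added variance is small, the pooled df is very large, and a model with 10 residual df is judged almost as if the sample were large.

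The result is also inconsistent within the plan. Cohort 2 with no missing height, analysed directly in PROC MIXED, is read against t on 10 df (2.23). The same cohort with one imputed height is read against about 1.96, so losing a measurement makes the criterion more lenient. Both sensitivity analyses in Section 14.2.2 use children with an observed Week 52 height: the per-protocol set requires one, and the second analysis is restricted to children without missing data. Both would therefore come straight from PROC MIXED on residual df. Primary and sensitivity results could then differ partly because of the reference distribution.

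**Working it through.** The plan states no df, alpha or power figure on this point, so there is none to reproduce. A two-sided 5% level is assumed from the 95% interval.

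**1. Residual df at minimum enrolment** (Sections 4.2, 4.6.2 and 14.2.1). The common parameters are intercept, treatment, age, sex, baseline AGV and baseline Z-score, which makes 6. Cohorts 1 and 2 add one stratum term, making 7. The overall model has 27 + 17 + 17 = 61 randomized children. It has five stratum levels (two, two and one), hence four stratum terms and 10 parameters.

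| Model | n − parameters | df | t critical value | 1.96 / t | 2·P(t > 1.96) |
|---|---|---|---|---|---|
| Cohort 1 | 27 − 7 | 20 | 2.086 | 0.94 | 6.4% |
| Cohort 2 | 17 − 7 | 10 | 2.228 | 0.88 | 7.8% |
| Cohort 3 | 17 − 6 | 11 | 2.201 | 0.89 | 7.6% |
| Overall | 61 − 10 | 51 | 2.008 | 0.98 | 5.5% |

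For a given pooled variance, the by-cohort intervals are thus about 6%, 12% and 11% too narrow against t on residual df. A reported p of 0.030 would become 0.042, 0.055 and 0.053 in Cohorts 1, 2 and 3. The last column is the limit in which imputation adds no variance.

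**2. Default pooled df.** The formula is df = (m − 1)(1 + 1/r)², where m is the number of imputations and r is the relative increase in variance due to imputation. The SAP gives neither, so both are assumed.
- m = 100, r = 0.02: 99 × 51² = 257,499
- m = 20, r = 0.05: 19 × 21² = 8,379
- m = 5, r = 0.10: 4 × 11² = 484
- m = 5, r = 1.0: 4 × 2² = 16

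The critical value stays at 1.96 to 1.98 unless missingness is heavy and m is small.

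**3. Small-sample (Barnard-Rubin) df.** With residual df v, the observed-data df is v(v + 1)/(v + 3) divided by (1 + r). This is combined with the default df as 1/(1/default + 1/observed). For Cohort 2 with m = 20 and r = 0.05, the observed-data df is (10 × 11/13)/1.05 = 8.06. The combined df is about 8.1 and the critical value 2.30. Over r = 0.05 to 0.20 with m = 20:

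| Cohort | df | Critical value | Wider than default |
|---|---|---|---|
| 1 | 17.4 to 14.9 | 2.11 to 2.13 | 7 to 9% |
| 2 | 8.1 to 7.0 | 2.30 to 2.37 | 17 to 21% |
| 3 | 9.0 to 7.8 | 2.26 to 2.32 | 15 to 18% |

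**4. Actual size.** Null trials were simulated with 5,000 per row, m = 30 and a seven-parameter ANCOVA. Missing values were imputed from a placebo regression on one earlier measurement, with assumed correlation ρ.

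| n | Missing | ρ | Default df | Barnard-Rubin df |
|---|---|---|---|---|
| 17 | 1 active | 0.80 | 5.3% | 2.7% |
| 17 | 1 active | 0.95 | 6.2% | 3.4% |
| 17 | 1 per arm | 0.80 | 4.6% | 2.0% |
| 17 | 1 per arm | 0.95 | 6.2% | 3.4% |
| 27 | 1 active | 0.80 | 5.4% | 4.1% |
| 27 | 1 active | 0.95 | 6.5% | 5.2% |
| 27 | 1 per arm | 0.80 | 4.6% | 3.1% |
| 27 | 1 per arm | 0.95 | 5.6% | 4.0% |

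Further runs with 1 to 2 missing and ρ from 0.5 to 0.95 gave 3.7 to 7.9% with the default and 1.6 to 5.6% with Barnard-Rubin. The extremes under other imputation set-ups were about 2.5% and 8.2% with the default.

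**The case against.** The strongest reply is that the SAP prints no MIANALYZE call. The infinite-df default is software behaviour and not SAP text, so the programmer could still set the option. That is fair as to wording. But Section 14.2.1 specifies the neighbouring step down to the LSMEANS options, and the plan followed as it stands gives the wrong reference for these models.

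A reader might infer from the limiting figures that the by-cohort tests run at 7.8% and are systematically anti-conservative. The documents do not support that. Size depends on an imputation model the SAP does not specify. Imputing from placebo data enlarges the pooled variance, and with two missing values and a moderate correlation the default test is often at or below 5%. The higher values come mainly from the assumed correlation of 0.95. This objection stands. The offset is accidental, however, and does not justify infinite df for a model with 10.

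The trigger is also narrow: no value in the Day 321 to 407 window and none later. The by-cohort models are planned as appropriate, without a stated alpha or decision rule, and enrolment above the minimum raises the df. These points limit the reach of the problem but do not remove it, because intervals and p-values are still to be reported. The sensitivity analyses do not isolate the effect, since they change the children analysed as well as the reference.

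**Conclusion.** The point holds in a limited form. Without a complete-data df, a by-cohort result that includes any multiply imputed Week 52 value is read against about 1.96, where residual df call for 2.09, 2.23 and 2.20 in Cohorts 1, 2 and 3. The shortfall in interval width is therefore conditional on the pooled variance. It is not a demonstrated type I error: limiting sizes are 6.4%, 7.8% and 7.6%, and actual size is about 4% to 8% in most assumed settings and sometimes lower. The overall model is barely affected, with a limiting size of 5.5% and an interval 2.4% wider on t with 51 df.

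This rests on four assumptions: minimum enrolment, the default df rule, a two-sided 5% level, and the values taken for m, r and the correlation with an earlier measurement. The inconsistency between analyses with and without imputed values does not depend on the simulations.

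**What to change.** Add a sentence to Section 14.2.1: PROC MIANALYZE is run with EDF= equal to the residual df of the corresponding PROC MIXED model, giving Barnard-Rubin df. Apply it to the overall model, each by-cohort model, the repeat that includes sentinel children, and every endpoint that uses imputed data. The value must be taken from each model. For example, the AGV model has no separate baseline-outcome term, so its minimum by-cohort df are 27 − 6 = 21, 17 − 6 = 11 and 17 − 5 = 12. The number of imputations should be stated in the same place.

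The cost is one option and one sentence, with no change to data, design or estimand. Pooled intervals become wider, by the amounts in step 3 for the by-cohort models. In the two smallest cohorts the test may be somewhat conservative when imputation variance is appreciable, with a corresponding loss of power.

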14.2.2 Sensitivity Analyses

The following sensitivity analyses will be conducted on the primary efficacy endpoint:

- (1) Model-based analyses on the subjects in the PP population
- (2) Model-based analyses on the subjects with no missing data at Week 52

14.3 Secondary Efficacy Endpoint(s)

14.3.1 Standing Height/Body Length

Rules for standing height/body length is described in Section [14.1](#).

The standing height/body length and its change from baseline will be summarized and presented separately by cohort by treatment group using the format as specified in [Table 5.1](#), [Table 5.2](#), and [Table 5.3](#) for Cohorts 1, 2, and 3, respectively.

Standing height/body length will be analyzed using the same methods and estimand formulation as the primary efficacy endpoint analysis and sensitivity analyses. An analysis of change from baseline in standing height/body length at Week 52 will be performed using an

ANCOVA model that includes the fixed-effects of treatment (active arm vs. placebo arm) and baseline covariates, where baseline covariates include randomization age stratum, age at baseline, sex, baseline AGV, and baseline standing height/body length.

Standing height/body length for all visits will be included in data listings including data from 111-901 and 111-206.

Spaghetti plots of standing height/body length at every 6 months assessments including height assessments collected in the 111-901 study (3-month prior for Subjects in Cohort 3) will be provided for each subject separately by cohort. This plot will include age-sex specific reference ranges for average stature children (from CDC, 2019) and age-sex specific reference ranges for short stature children (Hoover-Fong, 2021).

For these plots if body length is used for Cohort 1, it will be indicated in the plot. Likewise, if standing height is used for Cohort 2, it will be indicated in the plot.

A line plot of the mean (+/-SD) standing height/body length will be presented by cohort at 6 Months Prior (3-month prior for Subjects in Cohort 3), Baseline, Week 26 and Week 52.

14.3.2 Annualized Growth Velocity

For a given interval [Date1, Date2], the AGV is defined as follows:

$$\text{AGV (cm/yr)} = (\text{Derived Standing Height at Date 2} - \text{Derived Standing Height at Date 1}) / (\text{Interval Length (Days)} \times 365.25)$$

where the interval length in days is calculated as Date2 - Date1.

AGV (cm/yr) will be calculated at baseline, Week 26, and Week 52. AGV at baseline will be calculated by using height measurements in Study 111-901 6 months prior to Day 1 of Study 111-206 for subjects in Cohorts 1 and 2, and using height measures in Study 111-901 or 111-206 3 months prior to Day 1 of Study 111-206 for subjects in Cohort 3. AGV at other time points will be calculated cumulatively from Day 1 of 111-206 and every 6 months interval.

The absolute values for cumulative AGV and 6-month AGV and their change from baseline will be summarized and presented separately by cohort by treatment group using the format specified in Table 5.1, Table 5.2, and Table 5.3 for Cohorts 1, 2, and 3, respectively.

Cumulative AGV will be analyzed using the same methods and estimand formulation as the primary efficacy endpoint analysis and sensitivity analyses. An analysis of change from baseline in cumulative AGV at Week 52 will be performed using an ANCOVA that includes the fixed-effects of treatment (active arm vs. placebo arm) and baseline covariates, where

baseline covariates include randomization age stratum, age at baseline, sex, and baseline AGV.

A box and whisker plot will be provided for AGV (cm/yr) over time by cohort and treatment group. A line plot of individual cumulative AGV will be presented at baseline and Week 52 for each subject by cohort by stratified age stratum.

Listings for the cumulative AGV and 6 months AGV will include all calculated AGV.

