The exploratory objectives of the study are optional and will not be addressed in this SAP.

STUDY DESIGN AND PLAN: Study 111-206 is a phase 2 randomized, double-blind, placebo-controlled clinical trial of vosoritide in infants and younger children with a diagnosis of ACH.

Approximately 70 Subjects will be enrolled into 3 age cohorts: $n \geq 30$ total for aged ≥ 24 to < 60 months, $n \geq 20$ total for aged ≥ 6 to < 24 months, and $n \geq 20$ total for aged 0 to < 6 months.

There will be 3 sentinel subjects for each cohort, and the rest of subjects will be randomized 1:1 to treatment or placebo control and stratified by age for Cohorts 1 and 2.

All subjects who complete the 111-206 study will be eligible to receive vosoritide in the extension study 111-208 after the Week 52 visit.

ANALYSIS POPULATIONS:

The Full Analysis Set (FAS) is defined according to the intent-to-treat principle and includes all enrolled sentinel and randomized subjects with a signed informed consent.

The Per-Protocol (PP) population is defined as a subset of the FAS population who completed the treatment originally allocated (i.e., always received the assigned treatment), with a standing height/body length assessment at Week 52 following the protocol window, and with treatment compliance of at least 80%.

The Safety Population is a subset of the FAS who receive at least one dose of vosoritide or placebo in this study.

The PK Population is defined as all sentinel subjects and subjects randomized to vosoritide treatment group, who received at least one dose of vosoritide in this study and have at least one evaluable PK concentration.

The Immunogenicity Population is defined as all subjects in the Safety Population who have at least one evaluable immunogenicity sample.

STUDY ENDPOINTS AND ANALYSES:

Efficacy endpoints and analyses:

The primary efficacy endpoint is change from baseline in standing height/body-length Z-Score at Week 52.

The key secondary efficacy endpoints include change from baseline at Week 52 in standing height/body length, AGV, and upper to lower body ratio. Other secondary efficacy endpoints include biomarker samples to evaluate the effect of vosoritide on bone metabolism, vosoritide pharmacodynamic biomarkers, growth parameters and body proportions, sleep apnea, skull and brain morphology, and clinical outcome assessments (developmental/functional/HRQoL status).

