Appendix [25.1](#) provides details of the derivations used for each endpoint.

All efficacy endpoints will be assessed using the FAS.

Visit windows are applied for all assessments (see Section [5.4](#)) and are used to summarize the growth measures by visit.

All parameter assessments are considered for inclusion in analyses.

With the exception of AGV (see Section 14.3.2), summary tables for all growth measures including standing height/body length Z-Score, standing height/body length, upper to lower body segment ratio, body proportion ratios, other growth measures (see Section 14.3.5), BMI, BMI Z-Scores, and weight Z-Scores will include assessments at baseline, Week 26 and Week 52 from Study 111-206, and 6 months prior in Study 111-901. For subjects in Cohort 3 assessments at 3 months prior to baseline in Studies 111-206 or 111-901 will be included.

Each table will include summaries of the absolute observed measures and its change from baseline at each of these time points. The tables will summarize data separately by cohort by treatment group using format as specified in Table 5.1, Table 5.2, and Table 5.3 for Cohorts 1, 2, and 3, respectively.

ANCOVA models will be conducted for change from baseline at Week 52 in standing height/body length Z-Score, standing height/body length, AGV, and upper to lower body ratio for all cohorts overall and/or by cohort, as appropriate. Unless otherwise specified, all models will include the following baseline covariates: randomization age stratum, age at baseline, baseline AGV, and sex. Analyses of standing height/body length Z-Score, standing height/body length, and upper to lower body ratio will include their baseline as additional covariate.

For the model-based analyses, if the required assessment at Week 52 is missing but there are assessments before and after Week 52, a linear interpolation using the measurements closest to the before and after Week 52 will be used, otherwise those with no assessment after Week 52, multiple imputation by using placebo data from subjects in the same cohort (PROC MI) will be used to impute the missing values for standing height/body length and upper to lower body segment ratio at Week 52.

In addition to the primary analyses conducted on FAS, sensitivity analyses will also be conducted and are described in Section 14.2.

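### SAP Section 14.3.2 puts 365.25 in the AGV denominator, so AGV as defined is not in cm/yr and is too small by a constant 365.25² (about 133,408); hypothesis tests are unaffected

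*SAP*

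**What the plan says.** Section 14.3.2 of SAP Version 2.0 gives one formula for AGV over an interval from Date 1 to Date 2. The numerator is the difference in derived standing height. The denominator is a single closed bracket containing "Interval Length (Days)} \times 365.25" (the stray characters are typesetting code from the PDF reading). The next line fixes the unit of the interval: "where the interval length in days is calculated as Date2 - Date1". The unit claimed for the result is also explicit: "AGV (cm/yr) will be calculated at baseline, Week 26, and Week 52".

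The quantity is used in two ways:

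- **As an endpoint.** The synopsis says: "The key secondary efficacy endpoints include change from baseline at Week 52 in standing height/body length, AGV, and upper to lower body ratio".
- **As a covariate.** Section 14.1 says of the ANCOVAs that "all models will include the following baseline covariates: randomization age stratum, age at baseline, baseline AGV, and sex". Section 14.2.1 repeats this for the primary model: "baseline covariates include randomization age stratum, age at baseline, sex, baseline AGV, and baseline height Z-Score".

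AGV is also listed among the baseline growth measures in Section 9.

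No other place gives a different formula. Appendix 25.1 says only which height measurement feeds AGV at each age. The change log in Section 24 records added line plots for Section 14.3.2 but no change to the formula. Section 4 states that the SAP's analyses take precedence over the protocol's.

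**The concern.** A growth velocity in cm/yr from an interval in days is the daily rate multiplied by the number of days in a year. The printed bracket divides by that number instead. The name, the label and the day count all point to one intended meaning, and the formula does not deliver it.

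At stake are the numbers a reader will use to judge the size of the effect on growth velocity: baseline AGV, AGV at Week 26 and Week 52, LS means, the treatment difference and its confidence interval. P-values would not reveal the error, because a constant factor cancels from the test statistic. A programmer who corrects the formula silently departs from the plan. A validator who codes it as printed gets a different answer.

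**Working it through.** **Inputs.** The formula, the day-based interval and the cm/yr label come from Section 14.3.2. The SAP gives no numerical AGV to reproduce, so the growth increments below are assumptions chosen only for illustration. The ratio does not depend on them.

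**Unit check.**

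- Printed: (H2 − H1) / (days × 365.25). If 365.25 is read as days per year, the unit is cm·yr/day². If it is read as a pure number, the unit is cm/day. Neither is cm/yr.
- Needed: [(H2 − H1) / days] × 365.25, or equivalently (H2 − H1) / (days / 365.25). Either gives cm/yr.

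**Size of the discrepancy.** Needed ÷ printed = [(H2 − H1) × 365.25 / days] ÷ [(H2 − H1) / (days × 365.25)] = 365.25² = 133,407.5625.

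| Assumed growth | Interval | Printed formula | Annualised correctly (cm/yr) |
|---|---|---|---|
| 4 cm | 364 days | 0.0000301 | 4.014 |
| 5 cm | 364 days | 0.0000376 | 5.017 |
| 6 cm | 364 days | 0.0000451 | 6.021 |
| 2.5 cm | 182 days | 0.0000376 | 5.017 |
| 10 cm | 91 days | 0.000301 | 40.14 |

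The 364-day interval is Day 1 to the Week 52 target, Day 365, in Table 5.4.2. The 5 cm row is 5 / (364 × 365.25) = 5 / 132,951 = 0.0000376, against (5 / 364) × 365.25 = 5.017.

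**Effect on inference.** Write k = 1/365.25², so that printed AGV = k × true AGV.

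- *AGV as outcome.* Change from baseline in AGV is multiplied by k. The treatment difference, its standard error and its confidence limits are all multiplied by k, so t and p are unchanged.
- *AGV as covariate only.* Multiplying a continuous covariate by k multiplies its own coefficient by 1/k and leaves the fitted values alone. The treatment estimate, its confidence interval and p are unchanged.

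**Numerical check.** I fitted a simplified ANCOVA (treatment, age, sex, baseline AGV) to invented data for 61 subjects, which is the minimum number randomized under Section 4.2 (27 + 17 + 17).

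| Model | Quantity | AGV in cm/yr | AGV as printed |
|---|---|---|---|
| AGV change | Treatment difference | 0.4948 | 0.00000371 |
| AGV change | 95% CI | −0.1276 to 1.1173 | −0.00000096 to 0.00000838 |
| AGV change | t; p | 1.5926; 0.1169 | 1.5926; 0.1169 |
| Another outcome, AGV as covariate | Treatment estimate; p | 0.1856; 0.1415 | 0.1856; 0.1415 |

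The simulated values mean nothing in themselves. They show only what changes with the scale and what does not.

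**The case against.** **The bracket may be a reading artefact.** The point turns on the position of one bracket in a line that a program read from PDF. The bracket is balanced, and it is the same in Version 1.1 and Version 2.0. That is only modest reassurance, because the same reading process could err the same way twice, and Version 1.1 is superseded in any case. This objection stands as a reason to look at the source page. Against it, the SAP places its other scaling constants correctly outside the division: the factor of 100 in percent change (Section 5) and in compliance (Section 12).

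**The intent is obvious, and literal coding would be noticed.** This largely stands as to likelihood. Section 5 reports means to one decimal more than the data collected, so at ordinary precision every AGV would print as zero. A misplaced parenthesis is the likeliest explanation. It does not make the definition correct, and the rest of the SAP offers nothing to fall back on.

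**No hypothesis test is affected.** This stands in full. Because baseline AGV is a covariate in every model, a reader might infer that the primary Z-score comparison is compromised. It is not: rescaling a covariate by a constant leaves the treatment effect as it was. The same holds for height/length and for the segment ratio.

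**Conclusion.** The formula is wrong as written. Followed literally, it makes every AGV value, LS mean, treatment difference and confidence limit labelled cm/yr too small by a constant factor of 133,407.56. The factor follows from the printed grouping and the day-based interval alone. The growth figures used to illustrate it are assumptions.

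The damage is limited to reported AGV values and estimates. AGV test statistics and p-values are unchanged, and so are the treatment effects for the primary endpoint and the other modelled endpoints.

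A reader might also infer that the trial's AGV results were actually computed wrongly. The SAP does not show that: it contains no derivation program and no results. The correction is still needed, because this is the only definition the SAP gives for a key secondary endpoint. The conclusion depends on the bracket in the source PDF matching the text read here.

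**What to change.** In Section 14.3.2, replace the formula with:

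AGV (cm/yr) = [(derived height at Date 2 − derived height at Date 1) / (Date 2 − Date 1, in days)] × 365.25

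Record the change in Section 24. Confirm that the derivation program and any independent validation program use this form, for example by checking that 5 cm over 364 days returns 5.017. Check the bracket against the source PDF first.

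The cost is one line of text and a brief program check. It needs no new data, no change to any model and no change to the endpoint as intended.
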